**Please note that a delay of 14 days or more will require the patient to be withdrawn from study.**

**If a patient is admitted with neutropenic sepsis, prophylactic antibiotics e.g. ciprofloxacin, day 10 – 21 (with or without filgrastim or lenograstim) should be used for all subsequent cycles.**

If the platelet nadir (day 13 -17) is less than  $20 \times 10^9/L$ , then a **20% dose reduction** should be made on subsequent administration of carboplatin.

Patients will be required to attend hospital to receive Carboplatin as a day case.

**Figure 1: Blood Count Guide Prior to Treatment**

[figure not shown]
[figure not shown]

Figure 2: Treatment Flowchart

### **3.3 *Study population***

The population for this study are patients diagnosed with metastatic seminoma with IGCCCG good prognosis disease.

### **3.4 *Target accrual***

Up to 50 patients will be recruited into the study (assuming 5 patients may withdraw for reasons other than disease progression) over four years. 45 evaluable patients will be necessary to establish activity of Carboplatin AUC10 in this setting.

## **4.0 *Eligibility, subject selection and withdrawal***

### **4.1 *Inclusion Criteria***

1. Metastatic seminoma-IGCCCG good prognosis.
2. Glomerular filtration rate by EDTA clearance over 25 ml/min (a measured creatinine clearance using Cockcroft and Gault would be allowed if unable to perform EDTA clearance).
3. ECOG Performance status 0-3.
4. Normal Alpha-fetoprotein (All levels of Human chorionic gonadotropin and Lactate dehydrogenase are acceptable).
5. Males aged  $\geq 18$  and  $\leq 75$  years.
6. Able to give written informed consent prior to study entry.
7. Patients must be sterile or agree to use adequate contraception during the period of therapy.

### **4.2 *Exclusion Criteria***

1. Metastatic seminoma with any non-pulmonary visceral metastases.
2. Raised Alpha-fetoprotein.
3. Any previous chemotherapy or radiotherapy.
4. Currently enrolled in any other investigational drug study.
5. Other malignancy except basal cell.

### **4.3 *Subject recruitment and screening***

Participants will be identified when attending clinic visits by a research nurse/investigator that will screen patients for entry into the study. The possibility for study enrolment will be discussed and if appropriate, a patient information sheet will be provided by a member of the study team. The patient details should be entered onto the pre-screening log (initials, date of birth, pre-screening date). The patient should be given ample time to consider

entering the study. If the patient refuses to enter into the study, the reason (if applicable) should be recorded on the pre-screening log (refer to section 5.2 for registration procedure).

Patients from within the Anglian network will also be identified via a specialist testicular multidisciplinary team meeting which, is held fortnightly and attended by investigators and research nurses from different sites across the Anglian Network.

#### **4.4 *Withdrawal of subjects***

Patients will be informed that they have the right to withdraw from the study at any time, for any reason, without prejudice to their medical care. The primary reason (if available) for a patient's withdrawal from the study should be recorded on the case report form (CRF). The right of patients to refuse to participate without giving reasons and prejudicing their further treatment will be respected. Any patients who decide to withdraw their consent completely will have no further data collected. However, if the patient withdraws from trial treatment only their data may be followed-up for survival as long as the patient is happy to do so.

The investigator also has the right to withdraw patients from the study for any of the following reasons:

- Disease Progression.
- Occurrence of intolerable side effects.
- Non-compliance.
- A delay in treatment of 14 days or more.

At the time of withdrawal, all end of study procedures should be completed (as per schedule of assessments). The patient will remain in the study for the purposes of follow up and data analysis.

##### **4.4.1 *Data collection and follow up for withdrawn subjects***

CRFs should be sent to the Centre for Experimental Cancer Medicine, Barts Cancer Institute within one month of patient completing each cycle.

Subjects who are withdrawn are still evaluable for toxicity and efficacy if they have received at least one cycle of treatment and any data collected whilst receiving treatment will be used in the final analysis. Patients who are withdrawn from the study will be followed up for 2 years after treatment. Similarly, this follow up data will be used in the

final analysis. Any patients who decide to withdraw their consent will have no further data collected unless they have given express permission to do so.

## **5.0 Study procedures and schedule of assessments**

### **5.1 *Informed consent procedures***

It is the responsibility of the Investigator, or a suitably trained doctor delegated by the Investigator to obtain written informed consent from each subject prior to participation in this study, following adequate explanation of the aims, methods, anticipated benefits and potential hazards of the study. Ample time must be given for consideration by the patient before consenting to take part. The Investigator or co-investigator (designee) must also fully explain to the subjects that they are not obliged to enter the study but, that they may choose to opt for standard treatment. Alternatively, if they *do* wish to participate in the study they may withdraw at any time without giving a reason.

If new safety information becomes available and significantly changes the risk/benefit of the study, the patient information sheet and consent form will be reviewed and updated immediately. Patients who have been recruited into the study, including those already being treated, should be informed of the new information and given a copy of the revised information sheet and if necessary re-consent to continue in the study.

### **5.2 *Registration/study procedures***

Following screening evaluation and patient consent, the study registration form should be completed and faxed to the Car-PET Clinical Trial Coordinator. The patients initials, date of birth and date of consent will be recorded.

## 5.3 Treatment procedures

### 5.3.1 Pre-treatment investigations

The following investigations must be completed before the patient can begin treatment:

- Physical examination.
- Contrast-enhanced staging CT scan of chest, abdomen & pelvis within 28 days of study entry. NB: If clinician suspects patient to be eligible for trial they may only do the PET-CT scan as the CT element is sufficient for diagnosis. The PET-CT scan will have to be done regardless of have a contrast-enhanced CT scan performed before study entry.
- Full body PET-CT within 28 days of study entry.
- Glomerular filtration rate by EDTA clearance (a measured creatinine clearance using Cockcroft and Gault would be allowed if unable to perform EDTA clearance).
- Alpha-fetoprotein, Human chorionic gonadotropin and Lactate dehydrogenase\*.
- Hormone levels of Testosterone, Follicle-stimulating hormone (FSH) and Luteinizing hormone (LH).
- Full blood count.
- Urea electrolyte.
- Liver function tests.

*Please note that approximately **20mls (max)** of blood will need to be taken at this time for future research. Blood will be collected in three 7.5ml EDTA tubes containing anticoagulant. The patient will need to sign a separate consent form agreeing for their samples to be used for future research. Once consent has been obtained, the sample should be sent directly to The Orchid Tissue Bank lab using the post boxes to:*

Orchid Tissue Bank Manager  
Orchid Tissue Bank  
Centre for Experimental Cancer Medicine  
Barts Cancer Institute - a CR-UK Centre of Excellence  
Queen Mary University of London  
John Vane Science Centre  
[name]  
[name]

### 5.3.2 Investigations during and after treatment

- Physical examination on Day 1 ( $\pm$  3 days) of cycle 2-4\*.
- Full Blood Count, Urea electrolyte and Liver function tests on Day 1 ( $\pm$  3 days) of cycle 2-4\*.

- Alpha-fetoprotein (AFP), Human chorionic gonadotropin (hCG) and Lactate dehydrogenase (LDH) on Day 1 during cycle 1-4, Day 13-17 of cycle 1-4 and Day 17-21 of cycle 1.
- Full Blood Count repeated on Day 13-17 of cycle 1-4\*.
- Hormone levels of Testosterone, Follicle-stimulating hormone (FSH) and Luteinizing hormone (LH) at end of treatment and annually thereafter during the follow up period of the trial.
- PET-CT scan on Day 17- 21 after the first cycle.
- PET-CT within 28 days of completing treatment (may be contrast enhanced CT if negative PET – CT scan on Day 17-21 of the first cycle).
  - If complete metabolic response is demonstrated contrast enhanced CT at 1 year and 2 years post therapy.
  - If residual masses are present, a contrast enhanced CT should be performed at 2 months after the end of the treatment PET-CT scan and if the masses are greater than 3cm in diameter, surgery to remove them is recommended in accordance with current practices.
- If patients require surgery following their treatment, a contrast enhanced CT scan of the area must be performed **2-3 months after the surgery** has taken place.
- If CR by chemo +/- surgery a final contrast enhanced CT at 2 years.
- Thereafter CT scan only if clinically indicated.

\* ***Patients who have a complete response to AUC-10 following cycle 1 will receive 2 further cycles. Those who do not achieve a complete response will have a further 3 cycles.***

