## **3.0 Investigational plan**

### **3.1 Overall design**

This is a single arm phase II study to assess the safety, efficacy and toxicity of carboplatin AUC-10 in metastatic seminoma. Patients will be recruited from two sites.

Prior to the commencement of treatment, the patient should have a baseline PET-CT scan and a contrast enhanced CT scan performed within 28 days of study entry. Patients will be treated with carboplatin AUC-10 every 3 weeks (3 weeks=1 cycle) and on day 17-21 of the first cycle a repeat PET-CT scan will be performed. All PET-CT scans will be reviewed centrally and these results will determine how many further treatment cycles the patients will undergo. If the patient has a complete metabolic response [refer to Appendix 3], a further 2 cycles of carboplatin will be given, leading to a total of 3, and if the patient has not had a complete metabolic response but is responding, a further 3 cycles of carboplatin will be given [Refer to section 5.3.3 and page 20 (the table) for the timelines for the scans. Please refer to appendix 8 for the imaging protocol].

If no response is seen, then the patient will be taken off study and will receive conventional therapy using a cisplatin-based combination.

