**APPENDIX 2 – PET-CT RESPONSE DEFINITIONS FOR CLINICAL TRIALS\***

RESPONSE	DEFINITION	NODAL MASSES
CR	Disappearance of all evidence of disease	a. FDG-avid or PET positive prior to therapy; mass of any size permitted if PET negative b. Variably FDG-avid or PET negative; regression to normal size on CT
PR	Regression of measurable disease and no new sites	>50% decrease in SPD of up to 6 largest dominant masses; no increase in size of other nodes a. FDG-avid or PET positive prior to therapy; one or more PET positive at previously involved site b. Variably FDG-avid or PET negative; regression on CT
SD	Failure to attain CR/PR or PD	a. FDG-avid or PET positive prior to therapy; PET positive at prior sites of disease and no new sites on CT or PET b. Variably FDG-avid or PET negative; no change in size of previous lesions on CT
RELAPSED DISEASE OR PD	Any new lesion or increase by >50% of previously involved sites from nadir	Appearance of a new lesion(s) >1.5 cm in any axis, >50% increase in SPD of more than one node, or >50% increase in longest diameter of a previously identified node >1cm in short axis Lesions PET positive if FDG-avid lymphoma or PET positive prior to therapy

Abbreviations: CR, complete remission; FDG, [F] fluorodeoxyglucose; PET, positron emission tomography; CT, computed tomography; PR, partial remission; SPD, sum of produce of the diameters; SD, stable disease; PD, progressive disease.
		

\*As published in Journal of Clinical Oncology [6]

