### **PARTIAL RESPONSE (PR) (marker positive)**

More than 90% reduction in tumour markers and/or >50% reduction in tumour masses determined by radiology for at least 28 days following cessation of chemotherapy without normalisation of tumour markers.

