### **PARTIAL RESPONSE (PR) (marker negative)**

Normalisation of markers and residual mass (marker negative PR) for at least 28 days

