3.1 General Study Design and Plan

This is a single arm phase II study to assess the safety, efficacy and toxicity of carboplatin AUC-10 in metastatic seminoma. Up to 50 patients will be recruited into the study over four years (assuming 5 patients may drop out for reasons other than disease progression/intolerable side effects). 45 evaluable patients will be necessary to establish activity of carboplatin AUC10 in this setting. Patients will be recruited for 48 months. Patients will be followed up as part of the study for 2 years following completion of treatment. The end of the study will be 3 months after the date when the last patient has completed his final follow up visit.

Prior to the commencement of treatment, the patient should have a baseline PET-CT scan and a contrast enhanced CT scan performed within 28 days of study entry. Patients will be treated with carboplatin AUC-10 every 3 weeks (3 weeks=1 cycle) and on day 17-21 of the first cycle a repeat PET-CT scan will be performed. If the patient has a complete metabolic response (see Appendix 3 of the protocol), a further 2 cycles of carboplatin will be given, leading to a total of 3, and if the patient has not had a complete metabolic response but is responding, a further 3 cycles of carboplatin will be given.

If a patient is showing no response to treatment then the patient will be taken off study and will receive conventional therapy using a cisplatin-based combination.

Figure 1: Treatment Flowchart

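### The 5.3.2 note and 5.4 footnote 4 give three more AUC-10 cycles to every patient without a complete response, whereas protocol 3.1 and SAP 3.1 take non-responders off study for cisplatin-based therapy

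*Protocol*

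**What the plan says.** Protocol 3.1 gives two further cycles after a complete metabolic response on the repeat PET-CT. For the rest it sets a condition: "if the patient has not had a complete metabolic response but is responding, a further 3 cycles of carboplatin will be given". It then adds a third branch: "If no response is seen, then the patient will be taken off study and will receive conventional therapy using a cisplatin-based combination". SAP 3.1 repeats all three, including "If a patient is showing no response to treatment then the patient will be taken off study".

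The starred note in protocol 5.3.2 and footnote 4 of the 5.4 flowchart give two further cycles after a complete response and then state: "Those who do not achieve a complete response will have a further 3 cycles". Neither mentions that the patient must be responding, gives an off-study branch, or refers to 3.1.

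Section 5.3.3 separates metabolic complete remission from non-complete responders and describes the decision that depends on the report as three cycles or four.

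Section 4.4 opens its list with "The investigator also has the right to withdraw patients from the study for any of the following reasons". The list is disease progression, intolerable side effects, non-compliance and a treatment delay of 14 days or more. Lack of response is not on it.

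**The concern.** A non-responder is, by definition, a patient without a complete response. For that patient the two sets of text give opposite instructions: no more carboplatin and a switch of regimen, or three more cycles of carboplatin. Both are worded as treatment rules and both are current text.

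What is at stake is the treatment of an individual patient. A site that works from the schedule and its footnotes could continue a drug that the design section says to stop, and so delay the cisplatin-based therapy that the design section requires. It also touches the protocol's second aim, which is to reduce the number of patients needing four cycles: the same patient has four cycles under the notes and as few as one under 3.1.

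**Working it through.** **1. The rules side by side**

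| Status after cycle 1 | Protocol 3.1 and SAP 3.1 | 5.3.2 note and 5.4 footnote 4 |
|---|---|---|
| Complete (metabolic) response | 2 more cycles, 3 in total | 2 more cycles, 3 in total |
| Incomplete, responding | 3 more cycles, 4 in total | 3 more cycles, 4 in total |
| No response | 0 more; off study, cisplatin-based combination | 3 more cycles, 4 in total |

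The texts agree on the first two rows and conflict on the third.

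**2. Who falls in the third row**

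Progression is already a withdrawal reason in 4.4, so progressors have another route off carboplatin. That leaves chiefly the patient with stable disease, which Appendix 2 defines as "Failure to attain CR/PR or PD".

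**3. Size per affected patient**

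Inputs: 21-day cycles (3.1); scan on day 17-21 (3.1, 5.3.2), or up to one week after day 21 (5.4 footnote 3), so as late as day 28; central report within 3 weeks of the image being sent, or of the scan if done at the central site (5.3.3); withdrawal for a delay of 14 days or more (3.2, 4.4). I assume the image is sent on the day of the scan and that blood counts cause no delay.

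- Cycle starts: days 1, 1 + 21 = 22, 22 + 21 = 43, and 43 + 21 = 64.
- Report before cycle 2: excess = 3 − 0 = 3 cycles, or 3 × 3 = 9 weeks.
- Scan on day 17-21 and the full 3 weeks used: report on day 17 + 21 = 38 to 21 + 21 = 42. Holding cycle 2 for it would mean a delay of 38 − 22 = 16 to 42 − 22 = 20 days, beyond the 14-day limit. If cycle 2 is therefore given first, the excess is 2 cycles, or 2 × 3 = 6 weeks.
- Scan on day 28 and the full 3 weeks used: report on day 28 + 21 = 49, after cycle 3 is due on day 43. The excess is then 1 cycle, or 3 weeks.

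The report table in 5.3.3 also lists a contrast-enhanced CT after cycle 2, where applicable. That scan, the markers or progression could end treatment sooner, so these are upper bounds.

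**4. Effect on the design**

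The plan's figures reproduce by exact binomial: P(X ≥ 39 | n = 45, 0.75) = 0.0446 and P(X ≥ 39 | n = 45, 0.90) = 0.8415, and 45 / (1 − 0.10) = 50. The cycle rule enters none of them.

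**5. Which criteria identify no response**

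Section 5.3.3 adopts the lymphoma criteria, tabulated in Appendix 2 as complete remission, partial remission, stable disease and progression. Section 3.1 and the 5.4 asterisk point instead to Appendix 3, which is headed as conventional CT response. Its partial response definitions carry time conditions: "determined by radiology for at least 28 days following cessation of chemotherapy" when markers remain positive, and "Normalisation of markers and residual mass (marker negative PR) for at least 28 days" when they do not. Its stable disease needs at least one month after chemotherapy. These conditions do not fit a scan made at the end of cycle 1. Usable categories therefore exist in Appendix 2. What the visible text lacks is a sentence saying which of them mean no response.

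**The case against.** The best defence is that the two notes are schedule footnotes. In 5.3.2 the asterisk hangs on assessments for cycles 2 to 4, and in 5.4 the superscript hangs on the cycle 2-4 column. They explain why not everyone has a cycle 4 visit, and a patient taken off study after cycle 1 has no such visit to annotate. The treatment rule is in 3.1, is mandatory and is repeated in the SAP, so harm requires a site to follow a footnote over the design section. This is plausible and lowers the likelihood of harm. It does not remove the conflict: the sentence has no limit to patients staying on study, and 5.3.3 repeats the two-way choice.

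A second defence is that, on one parse, progressive disease in Appendix 3 includes any patient whose markers fall by less than 50%. A stable scan without marker response might then count as progression, which 4.4 covers. The sentence can also be read as applying only after chemotherapy stops, so it is not a safe route.

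A reader might also infer more than the documents support:

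- That no response has no definition at all. Appendix 2 supplies categories, and the treatment flowcharts (protocol Figure 2, SAP Figure 1) are not visible, so nothing can be claimed about them.
- That sites would classify the same patient differently. Every PET-CT is centrally reviewed, and the report determines further cycles.
- That every stable-disease patient is a non-responder. Section 3.1 does not say so.
- That the chance of someone being affected can be quantified. The documents give no early non-response rate, and a count of non-responders would not be a count of patients mistreated.

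**Conclusion.** The conflict is real and should be fixed. Followed literally, the 5.3.2 note and 5.4 footnote 4 give a non-responder treatment that protocol 3.1 and SAP 3.1 rule out. The upper bound per affected patient runs from 3 excess cycles down to 1, depending on when the central report arrives. It rests on 21-day spacing, same-day image transfer and a site acting on the notes. Few patients are likely to be involved, though the documents give no figure. The primary analysis, sample size and error rates are untouched. The missing link between no response and the Appendix 2 categories is a secondary point of clarification.

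**What to change.** In the 5.3.2 note and 5.4 footnote 4, replace the second sentence with: *Patients without a complete response who are responding receive three further cycles; patients with no response come off study and receive cisplatin-based therapy (see section 3.1).* In 5.3.3, add the off-study option to the sentence that frames the decision as three or four cycles.

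As a clarification in 3.1, state which Appendix 2 categories on the centrally reviewed first repeat PET-CT count as no response, and in particular whether stable disease does. The Appendix 3 partial response and stable disease definitions should not be used for this decision with their 28-day and one-month conditions attached.

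The cost is one sentence in each of two notes, a phrase in 5.3.3 and one defining sentence in 3.1. No new scans, readers, data or patients are needed.

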### 5.3.3 Central review of PET-CT scans

There are currently no well validated metabolic response criteria for PET-CT in seminoma. Hence, we will use the criteria for assessment of response developed for the evaluation of lymphoma [6].

A Complete Response will be defined as **complete resolution** of all previously seen sites of nodal and metastatic disease. If residual sites of metastatic disease persist then the PET-CT will be used to evaluate metabolic activity.

Metabolic Complete Remission will be defined as the level of FDG uptake within the lesion that is no greater than normal mediastinal uptake these patients will receive 3 cycles in total. Lesions with uptake greater than the mediastinum will be viewed as non-complete

responders. The PET data will be viewed on standardised SUV (standardised uptake value) setting of between 0 and 5.0 and a visual comparison will be made to assess the degree of uptake within abnormal tissue [7]. These criteria will have a high probability of distinguishing true complete responders from partial responders. Contrast enhanced CTs will be evaluated via the standard response criteria (Appendix 4).

All PET-CT scans will be centrally reviewed at University College London Hospital. The results from the report will be used to determine the number of further treatment cycle's patients will require, following cycle 1. Copies of locally reported scans (where relevant) should be sent to the central reviewer via the secure NHS Image Exchange Portal system (IEP) for review by the central reviewer (please refer to appendix 7). Sending images via IEP will not apply to sites where patients are scanned at UCLH, however, sites must ensure that the proforma is completed and sent to remind the central reviewer. In addition to sending images via the secure IEP system, sites must email a copy of the Proforma Request form (see Appendix 5 and 6) that is appropriate to each site) to the central reviewer to indicate that an image has been sent via IEP.

The central reviewer will review the image and return the generated report within the appropriate timelines as stated in the table below (see Appendix 7);

All scans for central review to be sent to;

[name]

Consultant in Nuclear Medicine

Institute of Nuclear Medicine, T5

University College Hospital

[name],

[name]

[contact]

Proforma Request form to be emailed to: [[contact]](mailto:[contact]) and  
[[contact]](mailto:[contact])

The central review reporting of the Baseline and Day 17-21 PET-CTs will take place **within 3 weeks** of the site either sending image or the patient having their scan done at UCLH. **The PET-CT scans must be received within this timeframe in order for the patient's response to treatment to be assessed and the decision on whether the patient receives 3 or 4 cycles can be made.**

Low dose attenuation correction CT will be performed at the time of the PET acquisition. Follow up conventional diagnostic CT scans from this point on should be received within two months of being performed.

Scan	Report to be received within
Baseline PET-CT & Baseline contrast enhanced CT	Within 3 wks of sending image/the PET scan (if done at UCLH)
Day 17-21	Within 3 wks of sending image/the PET scan (if done at UCLH)
Contrast enhanced CT performed post cycle 2 (if applicable)	Within 3 wks of sending image/the PET scan (if done at UCLH)
End of Treatment PET-CT or contrast enhanced CT	2 months
All other Contrast enhanced CTs as per follow up	2 months

If reports have not been received by the site within the timelines as detailed above, please follow the escalation process as detailed in Appendix 7.

